4.1.2 Medical History

The subject's complete history should be collected and recorded through review of medical records and by interview. Concurrent medical signs and symptoms must be documented to establish baseline severities. A disease history, including the date of initial diagnosis and list of all prior anticancer treatments, and responses and duration of response to these treatments, also will be recorded.

4.1.3 Adverse Events

The accepted regulatory definition for an AE is provided in Section 6.1 All medical occurrences from the time of first dose that meet this definition must be recorded. Important additional requirements for reporting SAEs are explained in Section 6.2.

4.1.4 Concomitant Medications and Therapy

All concomitant medications and procedures from within 21 days before the start of study drug administration through 30 days after the last dose of study drug should be documented.

4.1.5 Confirmation of Eligibility

Subject eligibility for enrollment will be assessed per Section 3.4. All screening procedures, unless otherwise indicated, should be completed within 21 days of the first dose of study drug.

4.1.6 ECOG Performance Status

The ECOG performance index is provided in Appendix 1.

4.1.7 Physical Examination, Vital Signs, Height & Weight

The screening physical examination will include, at a minimum, the general appearance of the subject, height (screening only) and weight, and examination of the skin, eyes,

ears, nose, throat, lungs, heart, abdomen, extremities, musculoskeletal system, nervous system, and lymphatic system.

Symptom-directed physical exams, including tumor assessments by palpation, will be done during the treatment period and at the safety follow-up visits.

Vital signs (blood pressure, heart rate, respiratory rate, and body temperature) will be assessed after the subject has rested in the sitting position.

4.1.8 Bone Marrow Aspirate and Biopsy

A bone marrow aspirate and biopsy will be done at screening or up to 30 days before the main screening procedures. Per the current response criteria (Rajkumar 2011), a bone marrow aspirate/biopsy will also be required at any time on study to confirm a complete response (CR). The baseline bone marrow aspirate/biopsy will used for immunohistochemistry and/or flow cytometry, cytogenetics, and FISH. Testing will be performed at the study center's local laboratory or other clinical laboratory listed on the investigator's form FDA 1572. De-identified copies of all bone marrow biopsy/aspirate results may be requested by the sponsor.

When available, any unused bone marrow tissue will be used for PD testing. PD testing will be done by the sponsor.

4.1.9 Electrocardiogram

Subjects should be in supine position and resting for \geq 10 minutes before study-related ECGs.

4.1.10 Urine Pregnancy Test

Pregnancy tests will be required only for women of childbearing potential. If positive, pregnancy must be ruled out by ultrasound. Testing will be done by the central laboratory.

4.1.11 Hematology

Hematology studies must include complete blood count (CBC) with differential and platelet and reticulocyte counts. Testing will be done by the central laboratory.

4.1.12 Serum Chemistry

Serum chemistry must include albumin, alkaline phosphatase, ALT, AST, bicarbonate, blood urea nitrogen (BUN), bone-specific alkaline phosphatase, calcium, chloride,

creatinine, C-terminal telopeptide, glucose, lactate dehydrogenase (LDH), magnesium, phosphate, potassium, sodium, total bilirubin, total protein, and uric acid. If an unscheduled ECG is done at any time, then an electrolyte panel (ie, calcium, magnesium, and potassium) must be done to coincide with the ECG testing. Testing will be done by the central laboratory.

4.1.13 Urinalysis

Urinalysis includes pH, ketones, specific gravity, bilirubin, protein, blood, N-terminal telopeptide, and glucose. Testing will be done by the central laboratory.

4.1.14 T/B/NK Cell Count

Flow cytometry testing will include CD3⁺, CD4⁺, CD8⁺, CD19⁺, and CD16/56⁺ cells. Testing will be done by the central laboratory.

4.1.15 Disease Markers

Testing for serum M-protein levels (by serum protein electrophoresis [SPEP] and serum immunofixation electrophoresis [SIFE]), serum free light chains (SFLC), urine M-protein levels (by urine serum protein electrophoresis [UPEP] and urine immunofixation electrophoresis [UIFE]), and serum β 2-microglobulin will be done by the central laboratory.

4.1.16 Hepatitis B and C Testing

Hepatitis serology testing must include hepatitis B surface antigen (HBsAg), hepatitis B surface antibody (HBsAb), anti-HBc, and hepatitis C (HCV) antibody. Since intravenous immunoglobulins (IVIG) may cause false positive hepatitis serology, subjects who are receiving prophylactic IVIG and have positive HBsAg or anti-HBc must have negative hepatitis B DNA to be eligible. In addition, any subjects testing positive for any hepatitis serology, must have PCR testing (see Appendix 5 and exclusion criterion #11). Testing will be done by local or central laboratory.

Refer to Section 3.7.2 and Appendix 5 regarding monitoring of subjects who are anti-HBc positive or have a known history of HBV.

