3.4.2 Exclusion Criteria

Subjects will be ineligible for this study if they meet **any** of the following criteria:

- 1. Plasma cell leukemia or circulating plasma cells $\ge 2 \times 10^{9}/L$
- 2. Prior malignancy, except for adequately treated basal cell or squamous cell skin cancer, in situ cervical cancer, or other cancer from which the subject has been disease free for ≥ 2 years or which will not limit survival to < 2 years. Note: these cases must be discussed with the Medical Monitor.
- 3. A life-threatening illness, medical condition or organ system dysfunction which, in the investigator's opinion, could compromise the subject's safety, interfere with

the absorption or metabolism of ACP-196, or put the study outcomes at undue risk.

- 4. Significant cardiovascular disease such as uncontrolled or symptomatic arrhythmias, congestive heart failure, or myocardial infarction within 6 months of screening, or any Class 3 or 4 cardiac disease as defined by the New York Heart Association Functional Classification, or QTc > 480 msec.
- 5. Malabsorption syndrome, disease significantly affecting gastrointestinal function, or resection of the stomach or small bowel, gastric bypass, symptomatic inflammatory bowel disease, or partial or complete bowel obstruction.
- 6. Any immunotherapy within 4 weeks of first dose of study drug.
- The time from the last dose of the most recent chemotherapy or experimental therapy to the first dose of study drug is < 5 times the half-life of the previously administered agent(s).
- 8. Prior exposure to a B-cell receptor (BCR) inhibitor (eg, Btk, phosphoinositide-3 kinase [PI3K], or Syk inhibitors) or BCL-2 inhibitors (eg, ABT-199).
- 9. Ongoing immunosuppressive therapy, including systemic or enteric corticosteroids for treatment of MM or other conditions. Note: Subjects may use topical or inhaled corticosteroids as therapy for comorbid conditions. During study participation, subjects may also receive systemic or enteric corticosteroids as needed for MM therapy or treatment-emergent comorbid conditions.
- 10. Grade ≥ 2 toxicity (other than alopecia) continuing from prior anticancer therapy including radiation.

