- 11. Known history of human immunodeficiency virus (HIV), serologic status reflecting active hepatitis B or C infection, or any uncontrolled active systemic infection. Subjects with hepatitis B core antibody positive who are surface antigen negative or who are hepatitis C antibody positive will need to have a negative PCR result before enrollment. Those who are hepatitis B surface antigen positive or hepatitis B PCR positive and those who are hepatitis C PCR positive will be excluded.
- 12. Major surgery within 4 weeks before first dose of ACP-196.
- 13. Known history of a bleeding diathesis (eg, hemophilia, von Willebrand disease)
- 14. History of stroke or intracranial hemorrhage within 6 months before the first dose of ACP-196.
- 15. Requires or receiving anti-coagulation with warfarin or equivalent vitamin K antagonist (eg, phenprocoumon) within 28 days of first dose of study drug.
- 16. Requires treatment with long-acting proton pump inhibitors (eg, omeprazole, esomeprazole, lansoprazole, dexlansoprazole, rabeprazole, or pantoprazole).
- 17. ANC < 0.75 x 10^{9} /L or platelet count < 50 x 10^{9} /L. For subjects with >50% marrow involvement with plasma cells, ANC < 0.50 x 10^{9} /L or platelet count < 30 x 10^{9} /L.
- Creatinine > 2.5 x institutional upper limit of normal (ULN); total bilirubin
 > 2.5 x ULN; and aspartate aminotransferase (AST) or alanine aminotransferase (ALT) > 3.0 x ULN.
- 19. Breastfeeding or pregnant.

20. Concurrent participation in another therapeutic clinical trial.

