3.7.2 Hepatitis B Virus Reactivation

Serious or life-threatening reactivation of viral hepatitis may occur in subjects treated with ACP-196. Therefore, subjects who are hepatitis B core antibody (anti-HBc) positive, or have a known history of hepatitis B virus (HBV) infection, should be monitored monthly with a quantitative PCR test for HBV DNA. Monthly monitoring should continue until 12 months after last dose of ACP-196. Any subject with a rising viral load (above lower limit of detection) should discontinue ACP-196 and have antiviral

therapy instituted and a consultation with a physician with expertise in managing hepatitis B. Insufficient data exist regarding the safety of resuming ACP-196 in subjects who develop HBV reactivation.

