## **1. INTRODUCTION**

The purpose of this statistical analysis plan (SAP) is to provide details of the safety and efficacy analyses that have been outlined within Protocol Amendment 2 for Study ACE-MY-001, which is entitled “An Open-label, Phase 1b Study of ACP-196 in Subjects with Multiple Myeloma” dated January 13, 2016. The original SAP based on same protocol was for interim safety clinical study report (CSR) to support the new drug application (NDA) in relapsed and refractory mantle cell lymphoma. This SAP is updated to include efficacy analysis. Any change to the planned analyses described in the final SAP will be documented in the clinical study report (CSR).

Separate reports will be generated for pharmacokinetic (PK) and pharmacodynamic (PD) data.

From here on, acalabrutinib (generic name for formerly ACP-196) will be used in place of ACP-196 in this document.

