## **3. STUDY OVERVIEW**

### **3.1 Study Design**

This study is a multicenter, open-label, randomized, parallel-group study to be conducted at approximately 20 sites in 2 countries (United Kingdom and United States). Forty subjects are planned to be randomized 1:1 into the following 2 cohorts to receive acalabrutinib, with or without dexamethasone:

- Cohort 1 (acalabrutinib monotherapy): acalabrutinib 100 mg bid continuously
- Cohort 2 (acalabrutinib + dexamethasone): acalabrutinib 100 mg bid continuously and 40 mg dexamethasone once weekly

Due to limited evidence of efficacy of acalabrutinib monotherapy in R/R MM subjects in this study, in a memo dated March 15, 2016 to all study sites, the enrollment was discontinued immediately and subjects who were randomized to receive acalabrutinib monotherapy were permitted to crossover to receive acalabrutinib + dexamethasone treatment.

One cycle is defined as a 28-day study treatment period. Treatment may be continued until disease progression (PD) or an unacceptable drug-related toxicity occurs. All subjects who discontinue study drug will have a safety follow-up visit 30 ( $\pm 7$ ) days after the last dose of study drug unless they have started another cancer therapy within that timeframe.

All subjects will have hematology, serum chemistry, and urinalysis safety panels done at screening. Once dosing commences (Day 1), all subjects will be evaluated for safety, including serum chemistry, and hematology, once weekly for the first 4 weeks, every 2 weeks in Cycle 2 and monthly thereafter. PK/PD testing will be done in Cycle 1 and Cycle 2. The end of trial is defined as the point when the last subject on the study exits the study for any reason.

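### Section 4.1.16 suggests that an HBsAg-positive, HBV DNA-negative subject on prophylactic IVIG can be eligible, while exclusion criterion 11 and the synopsis exclude every HBsAg-positive subject

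*Protocol*

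**What the plan says.** Section 4.1.16 (Hepatitis B and C Testing) gives a reason and a rule for subjects on prophylactic IVIG. The reason is that IVIG may turn hepatitis serology falsely positive. The rule is that those with "positive HBsAg or anti-HBc must have negative hepatitis B DNA to be eligible". The next sentence requires PCR for anyone with any positive hepatitis serology and refers to Appendix 5 and exclusion criterion 11.

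Criterion 11 in Section 3.4.2 says: "Those who are hepatitis B surface antigen positive or hepatitis B PCR positive and those who are hepatitis C PCR positive will be excluded". For hepatitis B, its negative-PCR route is open only to "Subjects with hepatitis B core antibody positive who are surface antigen negative". The synopsis carries the same criterion. Neither mentions IVIG.

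On precedence, Section 4.1.5 says "Subject eligibility for enrollment will be assessed per Section 3.4", and the lead-in to Section 3.4.2 ("Subjects will be ineligible for this study if they meet" any of the criteria) makes a single criterion decisive.

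Section 3.7.2 directs monthly HBV DNA monitoring at "subjects who are hepatitis B core antibody (anti-HBc) positive, or have a known history of hepatitis B virus (HBV) infection".

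**The concern.** The IVIG sentence treats HBsAg and anti-HBc alike: if either is positive, eligibility turns on HBV DNA. With the false-positive rationale in front of it, a site would reasonably take a negative DNA result as clearing an HBsAg-positive subject on IVIG. Criterion 11 requires that subject to be excluded whatever the DNA result.

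The rule concerns subject safety. The Amendment 2 summary says that hepatitis screening was added because HBV reactivation had occurred with Btk inhibitors, including in one subject on ACP-196. A subject admitted on the Section 4.1.16 reading who was anti-HBc negative and had no known HBV history would also fall outside the monitoring group named in Section 3.7.2.

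**Working it through.** No formula applies to the main point, so the check compares the texts case by case. Both are current: the Amendment 2 summary shows that the same amendment added Section 4.1.16 and revised criterion 11, so neither is superseded.

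For a subject on prophylactic IVIG:

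| Serology and HBV DNA | Section 4.1.16 | Criterion 11 and synopsis | Result |
|---|---|---|---|
| HBsAg positive, DNA negative | DNA condition met; eligibility implied | Excluded | Conflict |
| HBsAg negative, anti-HBc positive, DNA negative | DNA condition met | Not excluded (negative-PCR route) | Consistent |
| HBsAg or anti-HBc positive, DNA positive | Not eligible | Excluded | Consistent |

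The conflict is confined to the first row.

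**Strict reading.** Taken as a necessary condition only, Section 4.1.16 does not admit the first-row subject, and a site can comply with both texts by excluding. But criterion 11 already removes every HBsAg-positive subject, so requiring a negative DNA result of them changes no decision. The false-positive rationale has a use for HBsAg only if a negative DNA result can rescue a positive antigen.

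**Which text governs.** Section 4.1.5 refers eligibility to Section 3.4, and any one exclusion criterion there suffices. Criterion 11 therefore prevails.

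**Enrollment window.** The start is the protocol amendment, which the SAP Introduction describes as "dated January 13, 2016". The end comes from SAP Section 3.1: "in a memo dated March 15, 2016 to all study sites, the enrollment was discontinued immediately". From 13 January to 15 March 2016, a leap year:

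18 (rest of January) + 29 (February) + 15 (March) = 62 days.

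This is an upper bound. Section 7.2 requires IRB/IEC approval before changes are implemented, which would shorten it at each site.

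**The case against.** The strongest reply is that there is no formal contradiction. Section 4.1.16 says what an IVIG subject must have, not that having it is enough. A site that follows both texts excludes every HBsAg-positive subject. That is correct, and it limits the point to one of misleading wording.

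A second reply is that redundancy proves little here, because the next sentence of Section 4.1.16 also requires PCR of subjects whom criterion 11 already excludes. This has some force. But that sentence is a general testing instruction, whereas the IVIG sentence speaks of eligibility and gives a reason for doubting the positive result, so it invites the rescue reading in a way that the general instruction does not.

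Third, criterion 11 is cited one sentence later, and Section 3.4.4 requires eligibility to be confirmed before enrollment and a form exchange with the sponsor before cohort allocation. These make an error less likely. The cross-reference is attached to the PCR requirement, however, and does not say which text prevails.

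Fourth, the Appendix 5 footnotes for hepatitis serology and HBV PCR were not in the text available for this review and may clarify the rule. Nothing is claimed about them.

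Finally, the consequence is minor. That stands, and it bears on the weight of the point rather than on whether the inconsistency exists.

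**Conclusion.** The concern holds as a wording inconsistency in a safety eligibility rule. Section 4.1.16 implies a route to eligibility that criterion 11 and the synopsis close. Criterion 11 governs; Section 4.1.16 does not override it.

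The size is small. One serologic combination is affected, probably involving few if any subjects in a trial planned for 40, over at most 62 days of enrollment under this wording. Nothing in the documents shows that such a subject was screened or enrolled. Sample size, endpoints and planned analyses are untouched; the SAP's only hepatitis B output is a listing of test results (SAP Section 10.6.2). The conclusion rests on the visible body text, with the Appendix 5 hepatitis footnotes unchecked. It should be corrected because it is a safety rule and the correction is trivial.

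**What to change.** Delete the words *HBsAg or* from the IVIG sentence in Section 4.1.16. The sentence then covers anti-HBc only, and HBsAg-positive subjects are excluded throughout. Check that the Appendix 5 hepatitis footnotes agree.

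If an IVIG exception for HBsAg was intended, leave Section 4.1.16 as it is, write the exception into criterion 11 and the synopsis, and name those subjects in the monthly HBV DNA monitoring group of Section 3.7.2.

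The first option removes two words from one sentence; the second edits three places. Neither has an analysis cost. With enrollment stopped, the practical benefit is mainly a consistent record and clean wording if the text is reused.

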4.1.17 Skeletal Survey

Standard lateral radiograph of the skull, anterioposterior and lateral views of the spine, and anterioposterior views of the pelvis, ribs, femora, and humeri are required at screening or baseline (ie, before the first dose of study drug). Radiographic imaging and analysis will be performed at the study center's local laboratory or other clinical laboratory listed on the investigator's form FDA 1572.

4.1.18 Pharmacodynamics

Blood samples and bone marrow, when available, will be used for PD testing (eg, Btk occupancy and B-cell activation). Refer to the laboratory binder for instructions on collecting and processing these samples. Testing will be done by the sponsor.

4.1.19 Pharmacokinetics

Refer to the laboratory binder for instructions on collecting and processing these samples. Testing will be performed at the central clinical laboratory. Leftover plasma samples may be used for exploratory ACP-196 metabolite analyses. The PK sampling timepoints are provided in Table 4-1.

					HOURS P	OSTDOSE		
Cycle	Day	Predose	0.5 (±5 min)	0.75 (±5 min)	1 (±5 min)	2 (±10 min)	4 (±10 min)	6 (±10 min)
1	1	Х	Х	Х	Х	Х	Х	Х
	8	Х			Х			
	15	Х			Х			
	22	Х	Х	Х	Х	Х	Х	Х
	28	Х			Х			

Table 4-1.	Pharmacokinetic	Sample Schedule
------------	-----------------	-----------------

Note: These timepoints are relative to the morning dose.

4.1.20 Tumor Assessment

Baseline myeloma assessments will consist of:

- M-protein determination using both of the following procedures:
 - serum protein electrophoresis (SPEP) and serum immunofixation electrophoresis (SIFE)
 - Urine protein electrophoresis (UPEP) and urine immunofixation electrophoresis (UIFE), all using the same 24-hour urine collection
- SFLC

- Plasmacytoma evaluation
- Bone marrow to quantify percent myeloma cell involvement (aspirate and biopsy required at baseline)
- Skeletal survey: lateral radiograph of the skull, anterioposterior and lateral views of the spine, and anterioposterior views of the pelvis, ribs, femora, and humeri
- β2-microglobulin

On-study myeloma assessments will consist of:

- SPEP and/or UPEP (if results were measurable at baseline); quantitative immunoglobulins if used to follow disease; immunofixation to confirm a complete response
- SFLC
- Plasmacytoma evaluation (if only measurable disease at baseline)
- Bone marrow aspirate and/or trephine bone biopsy (to confirm a complete response or if clinically indicated).

4.1.21 Study Drug Accountability

See Section 7.7.

4.2 INVESTIGATOR'S ASSESSMENT OF RESPONSE TO TREATMENT

Subjects will be evaluated by investigator review for disease response and progression according to the current guidelines proposed by the International Myeloma Workshop Consensus Panel 1 (Rajkumar 2011) and European Group for Blood and Marrow Transplant (EBMT; Bladé 1998)as listed below in . Response categories include sCR, CR, VGPR, PR, SD, and progressive disease. In addition, the number of subjects achieving the response category of MR will also be evaluated and reported. Subjects will be considered evaluable for response if they have a baseline and ≥1 adequate on-study myeloma assessment obtained ≥4 weeks from the start of therapy.

 Table 4-2. Response Criteria (derived from Rajkumar 2011 and Bladé 1998)

Response Subcategory	Re	esponse Criteria ^a
Complete response (CR)	•	Negative immunofixation of serum and urine and
	•	Disappearance of any soft tissue plasmacytomas and

Product: ACP-196 (acalabrutinib) Date: 13 January 2016 Protocol: ACE-MY-001

	 < 5% plasma cells in bone marrow^b.
Stringent complete response (sCR)	 CR as defined above plus Normal FLC ratio and Absence of clonal plasma cells by immunohistochemistry or 2- to 4-color flow cytometry.
Very good partial response (VGPR)	 Serum and urine M-component detectable by immunofixation but not on electrophoresis or ≥ 90% reduction in serum M-component plus urine M-component < 100 mg per 24 h.
Partial response (PR)	 ≥ 50% reduction of serum M-protein and reduction in 24-h urinary M-protein by ≥ 90% or to < 200 mg per 24 h If the serum and urine M-protein are not measurable, a ≥ 50% decrease in the difference between involved and uninvolved FLC levels is required in place of the M-protein criteria If serum and urine M-protein are not measurable, and serum free light assay is also not measurable, ≥ 50% reduction in bone marrow plasma cells is required in place of M-protein, provided baseline percentage was ≥ 30% In addition to the above criteria, if present at baseline, ≥ 50% reduction in the size of soft tissue plasmacytomas is also required
Minimal response (MR)	 Requires all of the following: ≥ 25% to ≤ 49% reduction of serum M-protein and 50% to 89% reduction in 24-hour urine M-protein and If present at baseline, 25-49% reduction in the size of soft tissue plasmacytomas and No increase in size or number of lytic bone lesions (development of compression fracture does not exclude response).
